9.1.2 SECONDARY EFFICACY ENDPOINTS

Refer to [Section 3](#) for definition and justification of endpoints.

The hypothesis testing of secondary endpoints will be conducted using a gatekeeping procedure based on a closed fixed-sequence test, provided the primary endpoint comparison is statistically significant. Additionally, the truncated Hochberg adjustment ($\gamma=0.80$) will be utilized to control for potential multiple dose comparisons for each endpoint. This procedure controls the study-wise type I error at the 0.05 significance level as described below.

In order to evaluate a dose comparison at each step, all preceding comparisons are to be statistically significant in favor of SYD-101 for that dose, ie, for a given endpoint, comparisons will only be

performed for the SYD-101 dose(s) that are statistically significant for the prior endpoint assessed. If both SYD-101 dose comparisons are statistically significant for the prior endpoint, the truncated Hochberg adjustment ($\gamma=0.80$) will be used to control type I error between the two doses for the given endpoint. Based on the truncated Hochberg adjustment with truncation parameter $\gamma=0.80$, if both dose comparisons were significant in the prior step, alpha of 0.05 is retained to the next step. In that step the truncated Hochberg adjustment will again be applied if there are two dose comparisons for the given step. However, if in the prior comparison, only one dose comparison of two comparisons was significant, then alpha of 0.005 is retained and the one dose comparison must yield a P value < 0.005 to be significant.

For the EMA submission, the SYD treatment arms will be combined and compared to vehicle for endpoints assessed on subset of fast progressors. For those endpoints, the one comparison will be assessed at the alpha level retained from the prior comparison (either 0.05 if both dose comparisons were significant for both doses for all prior endpoints assessed or 0.005 if only one dose comparison was significant for the prior endpoint assessed.)

Again, no correction for multiplicity for the different efficacy analysis for EMA and for FDA is required.

Table 9-4 summarizes all efficacy endpoints in order of testing for the EMA and FDA analyses.

Table 9-4: Order of Testing Efficacy Endpoint for EMA and FDA Analyses

| Endpoint | EMA | FDA |
|---|---|---|
| 1. Primary Efficacy Endpoint | Mean annual progression rate of myopia through month 24 Truncated Hochberg to control alpha for the two pairwise SYD to Vehicle comparisons | Proportion of participants with myopic progression >0.75 D at or before Month 36 Truncated Hochberg to control alpha for the two pairwise SYD to Vehicle comparisons |
| 2. Key Secondary Efficacy Endpoint | Proportion of participants with myopic progression >0.75 D at or before Month 24 Truncated Hochberg to control alpha for the two pairwise SYD to Vehicle comparisons | Mean annual progression rate of myopia through month 36 Truncated Hochberg to control alpha for the two pairwise SYD to Vehicle comparisons |
| Other Secondary Efficacy Endpoints | | |
| 3. | Proportion of participants with annual myopia progression rate through Month 24 ≤ 0.50 D/year Truncated Hochberg to control alpha for the two pairwise SYD to Vehicle comparisons | Proportion of participants with annual myopia progression rate through Month 36 ≤ 0.50 D/year Truncated Hochberg to control alpha for the two pairwise SYD to Vehicle comparisons |

| Endpoint | EMA | FDA |
|----------|---|---|
| 4. | 
Proportion of participants with annual myopia progression rate through Month 24 ≤ 0.25 D/year
 
Truncated Hochberg to control alpha for the two pairwise SYD to Vehicle comparisons
 | 
Proportion of participants with annual myopia progression rate through Month 36 ≤ 0.25 D/year
 
Truncated Hochberg to control alpha for the two pairwise SYD to Vehicle comparisons
 |
| 5. | 
Proportion of participants with increase of myopia of >0.50 D at or before Month 24
 
Truncated Hochberg to control alpha for the two pairwise SYD to Vehicle comparisons
 | 
Proportion of participants with increase of myopia of >0.50 D at or before Month 36
 
Truncated Hochberg to control alpha for the two pairwise SYD to Vehicle comparisons
 |
| 6. | 
Time to progression of myopia of >0.75 D through Month 24
 
Truncated Hochberg to control alpha for the two pairwise SYD to Vehicle comparisons
 | 
Time to progression of myopia of >0.75 D through Month 36
 
Truncated Hochberg to control alpha for the two pairwise SYD to Vehicle comparisons
 |
| 7. | 
Mean annual progression rate using Month 24 data on Subgroup of participants with refractive history of progression ≥ 0.5 D
 
If both dose comparisons are significant for prior endpoint, the SYD-101 0.01% and 0.03% arms will be combined for single comparison to vehicle at alpha retained from prior step. Otherwise, if only one treatment comparison is significant, then only that dose will be compared to vehicle using alpha retained from prior comparison
 | 
Mean change from baseline in axial length at Month 36 (at sites with the requisite equipment; at least 50% of participants)
 
Truncated Hochberg to control alpha for the two pairwise SYD to Vehicle comparisons
 |
| 8. | 
Mean annual progression rate using Month 24 data on Subgroup of participants with refractive history of progression ≥ 0.75 D
 
If both dose comparisons are significant for time to progression endpoint and the pooled dose comparison for prior endpoint was significant, the SYD-101 0.01% and 0.03% arms will be combined for single comparison to vehicle at alpha retained from prior step
 | |
| 9. | Mean change from baseline in axial length at Month 24 (at sites with the requisite equipment; at least 50% of participants) | |

| Endpoint | EMA | FDA |
|----------|---|-----|
| | Hochberg to control alpha for the two pairwise SYD to Vehicle comparisons | |

If the comparison is not statistically significant at any step, then remaining comparisons in the stated hierarchy will be considered nominal, descriptive, and exploratory. The study-wise type I error will be maintained with the above closed procedure. No type I error adjustment is required for the different primary endpoints between regulatory agencies as efficacy will be assessed independently in each submission.

Intercurrent events will be handled in the for the FDA and EMA key secondary estimands as presented in the table below.

Table 9-5: Summary of Intercurrent Event Handling for Key Secondary Estimands

| Intercurrent Event | Strategy for Key Secondary Estimands | Justification |
|---------------------------|---|--|
| Intermittent Missing Data | 
Hypothetical
 
 Intermittent missing data will be multiply imputed assuming data is missing at random (MAR) | Intermittent missing data are expected to be missing at random/due to logistical issues |
| Prohibited Treatment | 
EMA Composite
 
 Participants who receive prohibited treatment will be considered non-responders 
FDA Hypothetical
 
 Observations after receipt of prohibited treatment will be multiple imputed assuming MNAR using a sequential vehicle-based pattern regression. Observations after receipt of prohibited treatment will be removed for all treatment arms prior to imputation | Prohibited treatment includes therapies that have known efficacy for slowing myopia progression (eg, MiSight multifocal contact lenses, Ortho-K lenses, compounded atropine, etc.) and use may be uneven between the groups, and this could distort the treatment effect of SYD-101 to Vehicle |

| Intercurrent Event | Strategy for Key Secondary Estimands | Justification |
|---------------------------|---|--|
| Escape Medication | 
EMA Composite
 
 Participants who receive escape medication will be considered non-responders 
FDA Hypothetical
 
 Observations after receipt of escape medication will be multiple imputed assuming MNAR using a sequential vehicle-based pattern regression. Observations after receipt of escape medications will be removed for all treatment arms prior to imputation | 
The American Academy of Ophthalmology, among others, currently recommends low dose atropine for treatment of myopia progression. As escape medication use may be uneven between the groups, this could distort the medication effect of SYD-101 to Vehicle
 
If escape medication is initiated per protocol, it is not to be given until after the 2-year EMA endpoint. Additionally, escape criterion of 2.0 D progression is larger than the FDA endpoint defined progression > 0.75 D. However, if sites should choose to treat participants prior to the defined escape criteria being met, that would indicate a belief that participants have progressed
 |
| Treatment Discontinuation | 
Hypothetical
 
 Observations after DC due to a related AE will be multiply imputed assuming missing not at random (MNAR) using a sequential vehicle-based pattern regression Observations after Treatment DC for other reasons will be multiply imputed assuming MAR | 
Discontinuation due to related AE are labelled non-responders is a conservative strategy as the discontinuation is related to treatment. Other reasons for discontinuation will be considered to occur at random
 
Treatment policy will be used as a sensitivity analysis as this will reflect real world use including potential rebound effect when participants discontinue treatment
 |

| Intercurrent Event | Strategy for Key Secondary Estimands | Justification |
|-----------------------|---|--|
| Study Discontinuation | 
Hypothetical
 
 Observations after DC due to a related AE will be multiply imputed assuming MNAR using a sequential vehicle-based pattern regression Observations after DC for other reasons will be multiply imputed assuming MAR | 
This study was enrolling, and a large portion of participant follow-up was during the ongoing COVID-19 pandemic. The majority of study discontinuations are logistical due to withdrawal of consent
 
Discontinuation due to related AE are labelled non-responders and is a conservative strategy as the discontinuation is related to treatment. Other reasons for discontinuation will be considered to occur at random
 |
| Invalid SE Values | 
Treatment Policy
 
 Invalid SE values will be used | Given the age of children as participants, in clinical practice it would be expected to have non-ideal auto-refraction assessments |

For all other secondary endpoints secondary endpoints excepting axial length, time to progression, and the Fast Progression subgroups, intercurrent events will be handled as specified in the table below.

Table 9-6: Intercurrent Event Approaches for Secondary Estimands

[figure not shown]
| Intercurrent Event | Strategy for Secondary Estimands | Justification |
|---------------------------|---|---|
| Intermittent Missing Data | 
Hypothetical
 
 Intermittent missing data will be multiply imputed assuming data is missing at random (MAR) | Intermittent missing data are expected to be missing at random/due to logistical issues |
| Prohibited Treatment | 
Hypothetical
 
 Observations after receipt of prohibited treatment will be multiply imputed assuming MAR | Prohibited treatments include therapies that have known efficacy for slowing myopia progression (eg, MiSight multifocal contact lenses, Ortho-K lenses, compounded atropine, etc.) and use may be uneven between the groups and this could distort the treatment effect of SYD-101 to Vehicle |
| Escape Medication | 
Hypothetical
 
 Observations after receipt of escape medication will be multiply imputed assuming MAR | The American Academy of Ophthalmology, among others, currently recommends low dose atropine for treatment of myopia progression. As escape medication use may be uneven between the groups, this could distort |

| | | |
|---------------------------|---|--|
| | | the treatment effect of SYD-101 to Vehicle |
| Treatment Discontinuation | 
Hypothetical
 
 • Observations after DC due to a related AE will be multiply imputed assuming missing not at random (MNAR) using a sequential vehicle-based pattern regression • Observations after DC for other reasons will be multiply imputed assuming MAR | 
Discontinuation due to related AE are labelled non-responders is a conservative strategy as the discontinuation is related to treatment. Other reasons for discontinuation will be considered to occur at random
 
Treatment policy will be used as a sensitivity analysis as this will reflect real world use including potential rebound effect when participants discontinue treatment
 |
| Study Discontinuation | 
Hypothetical
 
 • Observations after DC due to a related AE will be multiply imputed assuming MNAR using a sequential vehicle-based pattern regression • Observations after DC for other reasons will be multiply imputed assuming MAR | 
This study was enrolling, and a large portion of participant follow-up was during the ongoing COVID-19 pandemic. The majority of study discontinuations are logistical due to withdrawal of consent
 
Discontinuation due to related AE are labelled non-responders and is a conservative strategy as the discontinuation is related to treatment. Other reasons for discontinuation will be considered to occur at random
 |
| Invalid SE Values | 
Treatment Policy
 
 • Invalid SE values will be used | Given the age of children as participants, in clinical practice it would be expected to have non-ideal auto-refraction assessments |

9.2 SAMPLE SIZE DETERMINATION

[figure not shown]
Group sample sizes of 280 in each treatment arm will achieve at least 90% power to detect a difference in the percentage of participants with myopic progression (>0.75 D) of at least 15% between a SYD-101 arm and Vehicle. Power calculations presented in Figure 9-1 are based on the Chi-squared test at a 2-sided significance level of 0.025.

Figure 9-1: Power for 2-Sided Chi-Square Test Evaluated at Alpha=0.025 for Proportion Responders When 280 Participants Per Arm

Additionally, group sample sizes of 280 per treatment arm achieves >90% power to detect a reduction of 0.18 D or more in the annual progression rate between SYD-101 and Vehicle, assuming a common SD of 0.60 D. Power calculations presented in Figure 9-2 are based on a 2-sample t-test evaluated at the 0.025 significance level.

Figure 9-2: Power for 2-Sided T-Test Evaluated at Alpha=0.025 for Annual Progression Rate When 280 Participants Per Arm

Calculations were performed using SAS® 9.3 Software (SAS Institute, Inc, Cary, North Carolina).

This study plans to continue follow-up for all enrolled participants through Month 48, regardless of early discontinuation of study treatment or receipt of escape medication/prohibited therapy. All participants will be included in analyses based on their observed data. Because the effect size estimates have already taken into consideration the impact of no therapy/escape medication, enrollment of additional participants beyond 280 participants per treatment arm has not been planned.

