| | Difference in mean annual progression rate of myopia through Month 24 between SYD-101 0.03% and Vehicle | Month 36 between SYD-101 0.01% and Vehicle Difference in proportion of participants with confirmed myopic progression >0.75 D at or before Month 36 between SYD-101 0.03% and Vehicle |
|--|---|--|

Intercurrent events will be handled in the same manner for both the FDA and EMA primary estimands as presented in the table below.

Table 9-2: Summary of Intercurrent Event Handling for Primary Estimands

| Intercurrent Event | Strategy for Primary Estimands | Justification |
|---------------------------|--|--|
| Intermittent Missing Data | Hypothetical 
 Intermittent missing data will be multiply imputed assuming data is missing at random (MAR) | Intermittent missing data are expected to be missing at random/due to logistical issues |
| Prohibited Treatment | EMA Endpoint: While on Treatment 
 MMRM using observed data until receipt of prohibited treatment (no multiple imputation) FDA Endpoint: Composite 
 Participants who receive prohibited treatment will be considered non-responders (eg, have progressed) | Prohibited treatments include therapies that have known efficacy for slowing myopia progression (e.g., MiSight multifocal contact lenses, Ortho-K lenses, compounded atropine, etc.) and use may be uneven between the groups, and this could distort the treatment effect of SYD to Vehicle |
| Escape Therapy | EMA Endpoint: While on Treatment 
 MMRM using observed data until receipt of prohibited treatment (no multiple imputation) FDA Endpoint: Composite 
 Participants who receive escape medication will be considered non-responders (eg, have progressed) | The American Academy of Ophthalmology recommends low dose atropine to reduce myopia progression. As escape medication use may be uneven between the groups, this could distort the treatment effect of SYD to Vehicle If escape medication is initiated per protocol, it is not to be given until after the 2-year EMA endpoint. Additionally, escape criterion of 2.0 D progression is larger than the FDA endpoint defined progression > 0.75 D. However, if sites should choose to treat participants prior to the defined escape criteria being met, that would indicate a belief that participants have progressed |

| | | |
|---------------------------|---|--|

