| Treatment Discontinuation | 
EMA Endpoint: Hypothetical
 
 • Observations after DC due to a related AE will be multiply imputed assuming missing not at random (MNAR) using a sequential vehicle-based pattern regression • Observations after Treatment DC for other reasons will be multiply imputed assuming MAR 
FDA Endpoint: Composite
 
 • Participants with discontinuation (DC) due to a related AE are non-responders • Observations after DC for other reasons will be multiply imputed assuming MAR | 
Discontinuation due to related AE are labelled non-responders is a conservative strategy as the discontinuation is related to treatment. Other reasons for discontinuation will be considered to occur at random
 
Treatment policy will be used as a sensitivity analysis as this will reflect real world use including potential rebound effect when participants discontinue treatment
 |
| Study Discontinuation | 
EMA Endpoint: Hypothetical
 
 • Observations after DC due to a related AE will be multiply imputed assuming MNAR using a sequential vehicle-based pattern regression • Observations after Treatment DC for other reasons will be multiply imputed assuming MAR 
FDA Endpoint: Composite
 
 • Participants with DC due to a related AE are non-responders • Observations after DC for other reasons will be multiply imputed assuming MAR | 
This study was enrolling, and a large portion of participant follow-up was during the ongoing COVID-19 pandemic. The majority of study discontinuations are logistical due to withdrawal of consent.
 
Discontinuation due to related AE are labelled non-responders and is a conservative strategy as the discontinuation is related to treatment. Other reasons for discontinuation will be considered to occur at random.
 |
| Invalid SE Values | 
Treatment Policy
 
 • Invalid SE values will be used | 
Given the age of children in participants, in clinical practice it would be expected to have non-ideal auto-refraction assessments.
 |

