| Sensitivity Analysis 2 FAS Treatment Policy for Prohibited and Rescue Treatments | Hypothetical Multiple imputation assuming MAR | Treatment Policy Use observed data | Treatment Policy Use observed data | Treatment Policy Use observed data | FDA Endpoint: Composite Participants with discontinuation (DC) due to a related AE are non-responders Observations after DC for other reasons will be multiply imputed assuming MAR EMA Endpoint: Hypothetical Observations after discontinuation (DC) due to a related AE will be multiply imputed assuming MNAR using a sequential vehicle-based pattern regression Observations after Treatment DC for other reasons will be multiply imputed assuming MAR | Treatment Policy Use observed data |

| Analysis | Intercurrent Events | | | | | |
|--|--|---|---|---|---|---|
| | Intermittent Missing Data | Receipt of Prohibited Treatment | Receipt of Escape Therapy | Treatment Discontinuation | Study Discontinuation | Invalid SE Values |
| Sensitivity Analysis 3 FAS MAR Tipping Point Add fixed values of c to SYD imputed values | Hypothetical Multiple imputation assuming MAR | Hypothetical Observations after receipt of prohibited medication will be multiply imputed assuming MAR | Hypothetical Observations after receipt of escape medication will be multiply imputed assuming MAR | Treatment Policy Use observed data | Hypothetical Multiple imputation assuming MAR | Treatment Policy Use observed data |
| Sensitivity Analysis 4 FAS MNAR – exclude prohibited and escape observations before MNAR | Hypothetical Multiple imputation assuming MAR | Hypothetical Observations after receipt of prohibited medication will be multiply imputed assuming MNAR using a sequential vehicle-based pattern regression | Hypothetical Observations after receipt of escape medication will be multiply imputed assuming MNAR using a sequential vehicle-based pattern regression | Treatment Policy Use observed data | Hypothetical Observations after receipt study discontinuation will be multiply imputed assuming MNAR using a sequential vehicle-based pattern regression | Treatment Policy Use observed data |

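### Protocol 9.2 justifies having no attrition allowance with an observed-data premise that the current primary estimands do not follow, so the 90% power figures hold only for 280 fully informative participants per arm

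*Protocol*

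**What the plan says.** Protocol 9.2 makes two power claims, both at two-sided alpha 0.025. For the binary endpoint: "Group sample sizes of 280 in each treatment arm will achieve at least 90% power to detect a difference" of 15 percentage points in progression beyond 0.75 D. For the annual rate, 280 per arm "achieves >90% power to detect a reduction of 0.18 D or more in the annual progression rate", with SD 0.60 D.

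It then explains why no one is added for attrition. Follow-up continues after discontinuation, escape or prohibited therapy. "All participants will be included in analyses based on their observed data". The stated reason follows: "Because the effect size estimates have already taken into consideration the impact of no therapy/escape medication", no enrolment beyond 280 per arm is planned.

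The current primary estimands (Protocol Tables 9-1 and 9-2 and Section 9.4.2; SAP 3.2 and 8.1.1) treat the data differently:

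- **EMA.** Data after prohibited or escape treatment are censored. Data after treatment or study discontinuation are imputed, vehicle-based for a related AE and MAR otherwise.
- **FDA.** Prohibited treatment, escape and related-AE discontinuation count as progression. Otherwise, "Observations after DC for other reasons will be multiply imputed assuming MAR".
- **Treatment policy.** For treatment discontinuation, Table 9-2 says: "Treatment policy will be used as a sensitivity analysis as this will reflect real world use". Table 9-3 lists this as Sensitivity Analysis 2, "FAS Treatment Policy for Prohibited and Rescue Treatments".

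SAP 4.1 repeats the two power claims without the 9.2 rationale. It adds simulations that allow for dropout, treatment discontinuation and escape. The reported case is 0.65 against 0.325 D/year, SD 0.55 and 7% loss per year. With 217 per arm it gives about 97% power (FDA) and 99.96% (EMA).

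**The concern.** The argument in 9.2 works only if data collected after a participant stops treatment enter the primary analysis as observed. Under the current estimands they mostly do not, so a participant who stops treatment but keeps attending still loses information for the primary comparison. The argument also says nothing about participants who leave the study. Dilution built into an effect size cannot stand in for a missing Month 24 or Month 36 refraction, and even Sensitivity Analysis 2 imputes after study discontinuation. Table 9-2 acknowledges such losses, mostly through withdrawal of consent.

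These are the headline power statements for both regulators' primary endpoints. They carry no attrition condition, and neither document gives power under attrition for the 0.18 D or 15-point differences.

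**Working it through.** **Inputs.** From Protocol 9.2: n = 280 per arm, two-sided alpha 0.025, 0.18 D/year with SD 0.60, and 15 points with no vehicle rate given in the text. From SAP 4.1: 7% loss per year and SD 0.55.

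**1. The plan's own figures.** For the annual rate, I used a two-sample t-test with noncentrality δ / (σ√(2/n)).

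- At n = 280: 0.18 / (0.60 × √(2/280)) = 3.55. The critical value is about 2.24, so power is 90.3%.
- At n = 277 power is 89.99%, so 278 are needed. The margin is 2 per arm.

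For the proportion, I used a pooled-variance chi-square: power = Φ{[|p1−p2| − 2.241√(2p̄(1−p̄)/n)] / √([p1(1−p1)+p2(1−p2)]/n)}.

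- The least favourable pair is 57.5% against 42.5%. It gives 90.7% at 280, and 274 are needed.
- Power is higher elsewhere, for example 94.2% at 75% against 60%.

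Both claims reproduce.

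**2. EMA claim with 7% loss per year.** The number informative at Month 24 is 280 × 0.93² = 242.

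| Information from dropouts | n | SD 0.60 | SD 0.55 |
|---|---|---|---|
| No loss | 280 | 90.3% | 94.8% |
| None recovered | 242 | 85.3% | 91.2% |
| Part recovered under MAR | 250-261 | 86.5-88.0% | 92.0-93.2% |

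The last row is an assumption. It uses visits at Months 6, 12, 18 and 24, monotone dropout and between-visit correlations of 0.5 to 0.9. The documents give no correlations. Escape should remove little more, because "If escape medication is initiated per protocol, it is not to be given until after the 2-year EMA endpoint".

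**3. If 0.18 D is already diluted.** Suppose all of the 7% per year is stopping therapy with no effect afterwards. Mean time on treatment over two years is (1 − 0.93²) / (2 × −ln 0.93) = 0.931. The undiluted effect is 0.18 / 0.931 = 0.193 D/year. Power at SD 0.60 and n = 242 is then 90.3%. If only half of that loss was built in, it is about 88-90% (n 242-256).

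**4. Under the planned truncated Hochberg rule** (both p < 0.045, otherwise one < 0.025). This was simulated with a shared vehicle arm, 0.18 D and SD 0.60.

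- Both doses effective: per-dose power is 93.3% at 280, 89.2% at 242 and 90.3-90.9% at 251-256.
- Other dose null: 90.6% at 280, and about 86-88% after loss.

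**5. Covariates.** Adjustment restores 90% at alpha 0.025 if it explains about 12.7% of variance (n = 242) or 7.6-9.5% (n = 251-256). The documents give no figure for this.

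**6. FDA claim.** With no recovery, n = 280 × 0.93³ = 225. Power depends on the vehicle rate:

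- about 89% near a vehicle rate of 77%, which is an assumption: P(rate > 0.25 D/year) for a Normal with mean 0.65 and SD 0.55
- 91.0% at 80% against 65%

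These are lower bounds for a fixed 15 points, because progression confirmed before dropout is kept.

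**The case against.** The strongest case on the other side has four parts.

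*The literal reason in 9.2 is the effect-size sentence; the observed-data sentence only precedes it.* This is correct and it matters. If 0.18 D was already reduced for stopping therapy, the EMA hypothetical estimand targets a larger effect, and applying attrition to 0.18 D counts part of the loss twice. Step 3 shows power of about 90% if dilution is complete. The documents do not say how much dilution was built in. The vehicle-based imputation after related-AE discontinuation pulls the other way, and no rate is given for that either.

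*No document pairs SD 0.60 with 7% per year.* This also stands. SAP 4.1 pairs 7% with SD 0.55, and there the claim of more than 90% survives. But 0.60 is the SD attached to the protocol's claim, and 7% is the only loss rate that either document gives.

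*The planned test is more powerful than the planning test.* This stands in part. With both doses effective, per-dose power is about 89-91% before covariate gain. With only one effective, it stays at about 86-88%.

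*SAP 4.1 already simulates dropout.* It does, but its reported case is 0.325 D/year, about 1.8 times 0.18 D. It does not support the minimum-effect claims, and it does not correct the wording in Protocol 9.2.

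**Conclusion.** This is a minor inconsistency in the stated power rationale. The arithmetic is not wrong. The treatment-policy premise in Protocol 9.2 contradicts the current primary estimands and leaves loss to follow-up uncovered. The 90% figures hold for 280 fully informative participants per arm.

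At 7% annual loss, EMA power for 0.18 D/year at alpha 0.025, unadjusted, is about 85-88% at SD 0.60 and at least 91% at SD 0.55, assuming 0.18 D is not already diluted. If it is fully diluted, power is about 90% at SD 0.60. The upper end of the 85-88% range rests on assumed visit correlations.

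A reader might infer two stronger conclusions, and the documents support neither:

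- *That the trial is underpowered.* At the sponsor's expected effect, the SAP simulation with attrition gives about 97% and 99.96% with only 217 per arm. A direct check of the EMA case (0.325 D, SD 0.55, 217 × 0.93² = 188 per arm) gives about 99.97%.
- *That the FDA claim fails under attrition.* This depends on a vehicle rate that the text does not give. At 80% against 65%, power stays at 91.0% even with nothing recovered. Escape, prohibited treatment and related-AE discontinuation are scored outcomes for FDA, so those participants are not lost.

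**What to change.** Keep 280 per arm.

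1. In Protocol 9.2, replace the observed-data sentence with a reference to Table 9-2. Say whether 0.18 D and 15 points already include dilution from stopping therapy.
2. In Protocol 9.2 and SAP 4.1, state that the 90% figures assume 280 evaluable participants per arm.
3. In both places, add power at 7% annual loss. For 0.18 D/year at alpha 0.025: about 85-88% with SD 0.60 and at least 91% with SD 0.55, before covariate adjustment and assuming no prior dilution. Give the 15-point figure at the sponsor's own assumed vehicle rate. Do not insert a worst-case FDA figure.
4. Cite the SAP 4.1 simulation with its inputs: 0.65 against 0.325 D/year, SD 0.55, 7% per year and 217 per arm.

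The cost is wording only. The stated power becomes conditional and, at SD 0.60, slightly less favourable. Sample size, tests and decision rule do not change.
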